8.3.1. Time Period and Frequency for Collecting AE and SAE Information

All AEs and SAEs will be collected from the signing the informed consent form (ICF) until the final safety follow-up visit at the timepoints specified in the SoA (Section 1.3). If prior to completing the 90-day safety follow-up period a subject begins a new cancer treatment, no further safety follow-up is required.

All SAEs will be recorded and reported to the Sponsor or designee immediately and under no circumstance should this exceed 24 hours, as indicated in Appendix 10.3. The investigator will submit any updated SAE data to the Sponsor or designee within 24 hours of it being available.

Investigators are not obligated to actively seek information on AEs or SAEs after conclusion of the study participation. However, if the investigator learns of any SAE, including a death, at any time after a subject has been discharged from the study, and he/she considers the event to be reasonably related to the study treatment or study participation, the investigator must promptly notify the Sponsor or designee.

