9.2.4.2. Treatment Emergent Adverse Events

All adverse events will be coded to a system organ class and a preferred term based on the Medical Dictionary for Regulatory Activities (MedDRA) version 24.0 or later.

Treatment-emergent adverse events (TEAEs) are defined as AEs with an onset date on or after the date of first dose of study treatment until 90 days after the last dose.

Subject incidence of all treatment-emergent adverse events, serious adverse events, adverse events leading to discontinuation of treatment, and fatal adverse events will be tabulated by system organ class and preferred term.

The number and percent of subjects reporting TEAEs will be evaluated overall and by dose level and will also be tabulated by severity and relationship to study treatment. The severity of each adverse event will be graded using The Common Terminology Criteria for Adverse Events (CTCAE) version 5.0 or later criteria.

For the Phase 1 component of the study, DLTs (if any) will be summarized by dose and will be listed separately.

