10.3.1. Definition of AE

AE Definition

- An AE is any untoward medical occurrence in a clinical study subject, temporally associated with the use of study treatment(s), whether or not considered related to the study treatment(s).
- NOTE: An AE can therefore be any unfavorable and unintended sign (including an abnormal laboratory finding), symptom, or disease (new or exacerbated) temporally associated with the use of study treatment(s).
- Progression of the cancer under study is not considered an adverse event unless it results in hospitalization or death.

Definition of Unsolicited and Solicited AE

- An unsolicited adverse event is an adverse event that was not solicited and that is communicated by a subject who has signed the informed consent. Unsolicited AEs include serious and nonserious AEs.
- Potential unsolicited AEs may be medically attended (ie, symptoms or illnesses requiring
 a hospitalization, emergency room visit, or visit to/by a healthcare provider). The subject
 will be instructed to contact the site as soon as possible to report medically attended
 event(s), as well as any events that, though not medically attended, are of concern.
 Detailed information about reported unsolicited AEs will be collected by qualified site
 personnel and documented in the subject's records.
- Unsolicited AEs that are not medically attended nor perceived as a concern by the subject will be collected during an interview with the subjects and by review of available medical records at the next visit.
- Solicited AEs are predefined local (at the injection site) and systemic events for which the subject is specifically questioned.

Events Meeting the AE Definition

- Any abnormal laboratory test results (hematology, clinical chemistry, or urinalysis) or
 other safety assessments (eg, ECG, radiological scans, vital signs measurements),
 including those that worsen from baseline, considered clinically significant in the
 medical and scientific judgment of the investigator (ie, not related to progression of
 underlying disease)
- Exacerbation of a chronic or intermittent pre-existing condition including either an increase in frequency and/or intensity of the condition

- Protocol Number: PAL-E602-001 Version 8.0, 24 August 2023
- New condition detected or diagnosed after study treatment administration even though it may have been present before the start of the study
- Signs, symptoms, or the clinical sequelae of a suspected drug-drug interaction

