- Signs, symptoms, or the clinical sequelae of a suspected overdose of either study treatment or a concomitant medication. Overdose per se will not be reported as an AE/SAE unless it is an intentional overdose taken with possible suicidal/self-harming intent. Such overdoses should be reported regardless of sequelae.

Events NOT Meeting the AE Definition

- Any clinically significant abnormal laboratory findings or other abnormal safety assessments that are associated with the underlying disease, unless judged by the investigator to be more severe than expected for the subject's condition
- The disease/disorder being studied or expected progression, signs, or symptoms of the disease/disorder being studied, unless more severe than expected for the subject's condition
- Medical or surgical procedure (eg, endoscopy, appendectomy): the condition that leads to the procedure is the AE
- Situations in which an untoward medical occurrence did not occur (social and/or convenience admission to a hospital)
- Anticipated day-to-day fluctuations of pre-existing disease(s) or condition(s) present or detected at the start of the study that do not worsen

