 very important that the investigator always make an assessment of causality for every
 event before the initial transmission of the SAE data to the Sponsor or its designee.
- The investigator may change his/her opinion of causality in light of follow-up information and send an SAE follow-up report with the updated causality assessment.
- The causality assessment is one of the criteria used when determining regulatory reporting requirements.

Follow-up of AEs and SAEs

- The investigator is obligated to perform or arrange for the conduct of supplemental
 measurements and/or evaluations as medically indicated or as requested by the Sponsor
 or its designee to elucidate the nature and/or causality of the AE or SAE as fully as
 possible. This may include additional laboratory tests or investigations,
 histopathological examinations, or consultation with other health care professionals.
- If a subject dies during participation in the study or during a recognized follow-up period, the investigator will provide the Sponsor or its designee with a copy of any postmortem findings including histopathology, if available.

- Protocol Number: PAL-E602-001 Version 8.0, 24 August 2023
- New or updated information will be recorded in the originally submitted documents.
- The investigator will submit any updated SAE data to Sponsor or its designee within 24 hours of receipt of the information.

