4.3 Safety Endpoints

Treatment-Emergent Adverse Events (TEAEs)

Adverse events (AE) will be coded using the Medical Dictionary for Regulatory Activities (MedDRA) dictionary v24.1 or later. Severity will be graded according to the National Cancer Institute (NCI) Common Terminology Criteria for Adverse Events (CTCAE) v5.0. All AEs, complaints, or symptoms that occur from the time of written informed consent

through the 90-day safety follow-up are to be recorded on the appropriate case report form (CRF).

A TEAE is any adverse event with an onset date on or after the date of first dose of study treatment through 90-day safety follow-up or the initiation of new anti-cancer therapy, whichever is earlier. TEAEs will be summarized in the safety analysis.

Dose-Limiting Toxicities (DLTs)

A dose-limiting toxicity (DLT) is defined as the occurrence of any of the events listed in Section 4.1.5 of the protocol that are assessed by the investigator to be possibly, probably, or definitely related to study treatment. The DLT window of observation for the purposes of dose escalation will be Cycle 1 defined as a subject receiving 3 doses of E-602 for monotherapy cohorts and 3 doses of E-602 and 1 dose of cemiplimab for combination therapy cohorts.

Exposure to Treatment

Exposure to E-602 and cemiplimab will be summarized separately. The following variables will be derived for each drug.

Total Treatment Duration will be calculated as:

Total Treatment Duration (days) = Date of Last Dose – Date of First Dose + 1

Total Treatment Duration (months) = $12 \times \text{Total Treatment Duration (days)}/365.25$

Actual Dose Administered (mg) will be calculated as:

Actual Dose Administered (mg) = Actual Cumulative Dose Administered up to the Date of Last Dose

Relative Dose Intensity (RDI) is the percentage of actual dose administered relative to the cumulative dose planned through to treatment discontinuation.

RDI will be calculated as follows:

$$RDI = 100\% x (d/D)$$

where d (mg) is actual total dose administered and D (mg) is cumulative dose planned. D is the cumulative dose that would be administered if there were no modification to dose or schedule.

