6.4.2 Adverse Events

All TEAEs will be summarized. For subjects who are still on study treatment, all TEAEs reported up to the data cutoff date will be included.

AEs with incomplete start date will be considered treatment emergent if:

- Day and month are missing, and the year is equal to or after the year of the first dose date of study treatment;
- Day is missing and the year is after the year of the first dose date of study treatment;
- Day is missing and the year is equal to the year of the first dose date of study treatment and the month is equal to or after the year of the first doe date of study treatment;
- Year is missing; or
- Start date is completely missing.

However, if the end date of the AE is before the first dose date of study treatment, the AE will not be treatment emergent regardless of the completeness of its start date. AEs reported in the CRF but not considered TEAEs will be listed.

All TEAEs and SAEs will be coded using the most current version of MedDRA and graded by the Investigator according to the NCI CTCAE v5.0. Frequencies and percentage of subjects reporting each PT will be presented by SOC and PT. For each subject, multiple events of the same PT will be counted once in the summary. For summaries involving severity, the worst grade among events of the same PT will be used. The following summary tables of subject incidence will be provided by study treatment:

- All TEAEs
- SAEs
- Treatment-related TEAEs
- Treatment-related TEAEs by Severity
- Treatment-related SAEs by Severity
- TEAEs by Maximum Severity
- SAEs by Severity
- Treatment-related SAEs by Severity
- Treatment-related SAEs
- SAEs leading to treatment discontinuation (E-602, cemiplimab, E-602 in combination with cemiplimab)
- TEAEs leading to treatment discontinuation (E-602, cemiplimab, E-602 in combination with cemiplimab)
- TEAEs leading to dose interruptions (E-602, cemiplimab, E-602 in combination with cemiplimab)

• TEAEs leading to study drug delays (E-602, cemiplimab, E-602 in combination with cemiplimab)

The summary tables will include SOC and PT, and where applicable, severity grade will be added. An overall summary table with the number and percentage in the major AE categories listed above will also be provided.

Listings of TEAEs, fatal TEAEs, SAEs, and TEAEs leading to treatment discontinuation will be provided. For subjects treated in Phase 1 Dose Escalation, DLTs, if any, will be listed.

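### TEAEs are defined by onset date alone, so a screening AE that worsens after dosing is left out of the TEAE tables unless the site opens a new record

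*Protocol*

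**What the plan says.** Protocol 9.2.4.2: "Treatment-emergent adverse events (TEAEs) are defined as AEs with an onset date on or after the date of first dose of study treatment", with the window closing 90 days after the last dose. SAP 4.3: "A TEAE is any adverse event with an onset date on or after the date of first dose of study treatment", with the window closing at the 90-day safety follow-up or at new anti-cancer therapy, whichever is earlier. Neither mentions an increase in grade.

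Collection starts earlier. Protocol 8.3.1: "All AEs and SAEs will be collected from the signing the informed consent form (ICF) until the final safety follow-up visit". SAP 4.3 agrees: "All AEs, complaints, or symptoms that occur from the time of written informed consent" are to be entered on the CRF. Screening may last 28 days.

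SAP 6.4.2 adds rules for deciding treatment-emergence, but only for incomplete start dates and for AEs that ended before the first dose. For everything that fails the test it says: "AEs reported in the CRF but not considered TEAEs will be listed".

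Protocol 10.3.1 treats worsening as reportable. "Exacerbation of a chronic or intermittent pre-existing condition" meets the AE definition when frequency or intensity increases. Ordinary fluctuations are excluded only for conditions "present or detected at the start of the study that do not worsen". On how an existing entry is changed, the nearest text in Protocol 10.3.3 is: "New or updated information will be recorded in the originally submitted documents".

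**The concern.** AE incidence by CTCAE grade is a primary endpoint in Phase 1 and a secondary endpoint in Phase 2. A toxicity that is mild in screening and becomes severe on treatment is a change these tables should show. Under an onset-only rule, whether it is shown depends on how the site enters it.

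The plan is also uneven. A medical-history condition that worsens on treatment can become a TEAE through 10.3.1. The same complaint, first noted a few days after consent and recorded as an AE, may not. Elsewhere the SAP leans towards inclusion: an AE with no start date at all counts as treatment-emergent unless it ended before the first dose. Leaving out a documented post-dose worsening does not fit that approach.

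Any error runs in one direction, towards understating toxicity.

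**Working it through.** The plan gives no figure to reproduce, so the check traces one event through the rules.

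**Step 1: the event.** Suppose an AE starts at Grade 1 on Day -5, is ongoing at first dose, and reaches Grade 3 after the second infusion.

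- (a) The site raises the grade in the existing record. Onset stays at Day -5, before first dose, so the event is not a TEAE under either document.
- (b) The site enters the exacerbation as a new AE. Onset is after first dose, so the event is a TEAE under both.

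Both entries are compatible with the text. Section 10.3.1 permits (b). Section 10.3.3 has no rule for a grade change within an event, and its sentence on updates leans towards (a).

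**Step 2: does another rule catch (a)?** The incomplete-date rules in SAP 6.4.2 do not apply, because the start date is complete. The end-date rule does not apply either, because the event did not end before first dose. The SAP's worst-grade rule works only on events already in the table, so it cannot bring this one in.

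**Step 3: which outputs are affected under (a)?**

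| Output | Worded as TEAE-only? | Event under (a) |
|---|---|---|
| All TEAEs; treatment-related TEAEs, also by severity; TEAEs by maximum severity (SAP 6.4.2) | Yes | Missing |
| TEAEs leading to discontinuation, interruption or delay (SAP 6.4.2) | Yes | Missing |
| AEs leading to discontinuation, fatal AEs (Protocol 9.2.4.2) | No | Can be counted |
| SAE tables (both documents) | No | Counted if serious |
| DLT evaluation (Protocol 4.1.5) | No | Assessed where applicable |
| Listing of AEs that are not TEAEs (SAP 6.4.2) | No | Shown |

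**Step 4: size.** The share of subjects affected is a x b x c, where:

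- a = share with an AE starting between consent and first dose;
- b = share of those whose AE worsens after first dose;
- c = share of such worsenings entered in the existing record.

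The documents give none of the three. Purely as an illustration, assume a and b each lie between 10% and 30%:

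- c = 100%: 0.10 x 0.10 = 1% to 0.30 x 0.30 = 9%, or 0.3 to 2.8 of 31 subjects and 0.06 to 0.54 of 6.
- c = 50%: 0.5% to 4.5%, or 0.2 to 1.4 of 31 and 0.03 to 0.27 of 6.
- c = 0%: none.

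These figures show how strongly the answer depends on unknown inputs; they are not an estimate. What is exact is the effect of one missed subject: 1/3 = 33.3 points in a three-subject cohort, 1/6 = 16.7 in a six-subject cohort, and 1/31 = 3.2 in a full Phase 2 cohort. Because the SAP counts a preferred term once per subject, an incidence row changes only if that subject has no other TEAE of the same term. The maximum-severity row changes unless another TEAE of that term has an equal or higher grade.

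**The case against.** The best defence is that 10.3.1 already makes worsening an AE in its own right. It also covers clinically significant laboratory results that worsen from baseline, and Protocol 8.2.5 requires clinically significant laboratory changes to be recorded as AEs. On that reading the exacerbation has its own post-dose onset and is a TEAE without any change. How a grade change is entered is normally a matter for CRF completion guidance, which Protocol 10.1.7 promises and which is not among the documents reviewed. In addition, the AE row in the schedule of activities appears to have no screening mark, so pre-dose records may be few; the extracted table layout is not reliable enough to rest anything on this.

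Much of this stands, and it is why the point is conditional. A reader might infer that a screening AE that worsens can never be treatment-emergent and disappears from all safety output. The documents do not support that: a new record is permitted and would be counted, the event is listed in any case, and the SAE tables are not limited to TEAEs. A reader might also infer that dose escalation is compromised. It is not, because a DLT is defined by the type of event, relatedness and Cycle 1, not by TEAE status.

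What does not stand is the claim that 10.3.1 closes the gap. It says that an exacerbation qualifies as an AE. It does not say that an AE already on file must be split when its grade rises. Two sites could follow the protocol and report the same worsening differently, and only one would reach the TEAE tables.

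**Conclusion.** The point holds as a conditional one. The onset-only definition in both documents leaves an AE that began in screening and rose in grade after dosing out of the TEAE-based tables whenever the site updates the existing record. This follows from a stated rule and is more than missing detail. The direction is clear: an undercount that varies with site practice. The size is not known, because the documents give no rate for pre-dose AEs, for their worsening, or for the way worsening is entered. The conclusion rests on the protocol and SAP as written and assumes that no unseen CRF guidance already requires a new record. The change is worth making because these tables report a primary Phase 1 endpoint, small cohorts make single subjects visible, and the correction is cheap.

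**What to change.** 1. In SAP 4.3 and 6.4.2, define a TEAE as an AE with onset on or after first dose, or with onset before first dose and an increase in CTCAE grade on or after first dose, within the end window already in use. Count it at its worst post-dose grade.
2. Make the same change in Protocol 9.2.4.2 at the next amendment. Until then, record the difference in SAP Section 8, which now states that there are no changes from the protocol.
3. State in the CRF completion guidance that a post-dose grade increase is recorded with its own start date. Without that date the added clause cannot be programmed.
4. Query existing records with pre-dose onset that were ongoing at first dose, so that subjects already treated are handled in the same way as later ones.

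The cost is one clause in each document, a CRF note and a small number of queries. The protocol edit needs IRB approval, which is why it should wait for an amendment made for other reasons. TEAE percentages may rise slightly.

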9.2.4.3. Laboratory Values

Descriptive statistics for laboratory test values and changes from baseline at each visit will be tabulated and, in some cases, presented graphically. Additional analyses based on shift from baseline in test values in multiples of the lower/upper limit of normal range (LLN/ULN) of a parameter will be detailed in the statistical analysis plan.

9.2.4.4. Vital signs

Vital sign parameters (blood pressure, pulse, and body temperature), oxygen saturation, and weight observed at each visit will be summarized along with the change values from baseline. Clinically important physical exam findings will be listed and summarized.

9.2.5. Efficacy analysis

The primary analysis for efficacy will be based on the cohort-specific efficacy evaluable analysis set. Sensitivity analysis may include pooling additional subjects treated in Phase 1 at the same dose level in the same tumor type.

For objective response rate (ORR), the Clopper-Pearson 80% and 95% confidence intervals (CIs) will be provided. Confidence intervals adjusting for the 2-stage nature of the design may also be provided.

Duration of response (DoR) will be calculated among responders (CR and PR). The Kaplan-Meier method will be used to estimate median DoR and the confidence intervals. Subjects who continue to respond at the time of the analysis will be censored at the last assessment of response.

Progression-free survival (PFS) is measured from the date of first study treatment dose until the first date when progressive disease (PD) is objectively documented or death from any cause. Subjects without PD or death will be censored at the last available tumor assessment. PFS will be summarized using the Kaplan-Meier method.

Overall survival (OS) is measured from the date of first study treatment dose until death. Subjects who are alive will be censored at the last known alive date. OS will be summarized using the Kaplan-Meier method.

